1.4. Sample size calculation

The power calculation is based on recent studies using multi-session cognitive training interventions compared to control training (19–21), focusing on immediate performance in the trained task. Based on these findings, we estimated an effect size of Cohen's d = 0.8. To detect an effect in the primary outcome (percentage of correct responses on the n-back task between the cognitive training and control PMR groups) using an independent t-test with a two-sided significance level of $\alpha = 0.05$ and a power of at least 80%, 60 participants are required. This includes 40 participants for the cognitive training groups (for secondary comparisons of training combined with anodal vs. sham tDCS) and 20 participants for the PMR group. Even though we intend to analyze the primary outcome using covariance models, a conservative t-test approach was chosen for the power calculation. The sample size was estimated using the R software's *pwr* package (https://cran.r-project.org/package=pwr, http://www.R-project.org). This monocentric clinical trial will enable us to calculate the sample size for a subsequent multicenter clinical trial applying tDCS-accompanied cognitive training.

2. Analysis sets

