1.2. Primary hypothesis

• Cognitive training, combined with either active or sham tDCS, will result in greater improvement in untrained working memory performance at post-assessment compared to the control group receiving PMR in post-COVID patients. This outcome is operationalized by the percentage of correct responses on the n-back task at post-assessment.

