4.1. Primary outcome

Untrained working memory performance at post-assessment, measured by the percentage of correct responses on the n-back task (23).

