4.2. Secondary outcomes

Secondary outcomes will be assessed at both post-assessment and follow-up with specific exceptions indicated by an asterisk (*). These include:

- Untrained working memory performance, measured by the percentage of correct responses on the n-back task [(23) *at follow-up assessment].
- Trained working memory performance, measured by the number of correctly recalled lists on the letter updating task (24).

Statistical Analysis Plan

"Neuromodulation through brain stimulation-assisted cognitive training in patients with post-COVID-19 cognitive impairment (Neuromod- COV): study protocol for a PROBE phase IIb trial" Acronym: Neuromod-COV

- Untrained visuospatial memory performance, measured by the number of reached goals on the virtual reality task (25).
- Working memory discrimination, measured by the d-prime scores on the n-back task (23,26).
- Health-related quality of life, measured by the PROPr scores (27) on the PROMIS® 29-Profile v2.1 (28).
- Subjective cognitive functioning, measured by the T-scores on the PROMIS® Cognitive Function Scale [short form 8a v2.0; (28)].
- Post-COVID functional status, measured by the total raw scores on the PCFS (29).
- Sleep efficiency levels, measured as the percentage of time spent asleep relative to total time in bed, as recorded by an actigraphy device (*at post-assessment).

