6.1. Primary analysis

• Treatment effects on the transfer task (n-back task) at post-assessment will be analyzed using a linear mixed-effects model. This model will include the n-back performance at post- and follow-up assessments (percentage of correct responses) as the dependent variable. Fixed effects will include group (cognitive training vs. PMR), measurement time point (post vs. follow-up) and task difficulty (1-back vs. 2-back). Control covariates will include the n-back performance at pre-assessment (percentage of correct responses), age, and sex. A random intercept for subjects will also be included. The primary outcome (immediate transfer effects at post-assessment) will be estimated via marginal means (95% CI) from this model.

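### Section 1.4 estimates d = 0.8 from trained-task studies but claims at least 80% power for the n-back primary outcome, which the SAP defines as untrained transfer

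*SAP*

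**What the plan says.** Section 1.4 says that the power calculation draws on multi-session training studies, "focusing on immediate performance in the trained task", and that d = 0.8 was estimated from them. The next sentence applies this value to another outcome: "To detect an effect in the primary outcome (percentage of correct responses on the n-back task", compared between training and PMR. With a two-sided t-test at 0.05 it concludes that for "a power of at least 80%, 60 participants are required", split 40 to the two training arms together and 20 to PMR. It adds that, although covariance models are planned, "a conservative t-test approach was chosen for the power calculation".

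The rest of the SAP keeps trained and untrained performance apart:

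- Section 1.2, primary hypothesis: "greater improvement in untrained working memory performance at post-assessment compared to the control group receiving PMR".
- Section 4.1, primary outcome: "Untrained working memory performance at post-assessment, measured by the percentage of correct responses on the n-back task".
- Section 6.1 names the n-back as the transfer task and glosses the primary outcome accordingly: "The primary outcome (immediate transfer effects at post-assessment".
- Section 4.2 lists, among the secondary outcomes: "Trained working memory performance, measured by the number of correctly recalled lists on the letter updating task".

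**The concern.** An effect size estimated from performance on the task that people practised describes the gain in the practised skill. The primary hypothesis concerns a task that they did not practise. Section 1.4 moves from the first to the second in consecutive sentences and does not say how 0.8 relates to the untrained n-back. The remark that the t-test is conservative does not fill this gap. It concerns the residual variance left by the analysis, not the outcome from which d was taken.

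What is at stake is how the primary result is read, above all if it is not significant. A reader would take the trial as having at least 80% power for a transfer effect, and might treat a null result as evidence that training does not transfer. Section 1.4 also says that this trial will inform the sample size of a later multicenter trial, so an effect size tied to the wrong outcome could be carried forward.

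**Working it through.** **Inputs.** From section 1.4: d = 0.8; independent t-test; two-sided α = 0.05; n₁ = 40 (training), n₂ = 20 (PMR). Assumed here, because the SAP gives neither: alternative values of d for the n-back (0.7, 0.6, 0.5, 0.4) and pre-post correlations r (0.3, 0.5, 0.7).

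**Formula.** Power of the two-sample t-test from the noncentral t distribution with df = 40 + 20 − 2 = 58 and noncentrality d × √(n₁n₂/(n₁+n₂)) = d × √(800/60) = 3.651 d. The critical value is t(0.975, 58) = 2.002.

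**Step 1: the SAP's figure.** At d = 0.8 the noncentrality is 3.651 × 0.8 = 2.92 and power is 81.9%. A 2:1 total of 57 (38 versus 19) gives 79.9%, so 60 is the smallest 2:1 total that reaches 80%. The stated sample size reproduces.

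**Step 2: the same t-test at other effect sizes, 40 versus 20.**

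| d for the n-back (assumed, except 0.8) | noncentrality | power |
|---|---|---|
| 0.8 | 2.92 | 81.9% |
| 0.7 | 2.56 | 71% |
| 0.6 | 2.19 | 58% |
| 0.5 | 1.83 | 43% |
| 0.4 | 1.46 | 30% |

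Solving for 80% power gives a smallest d of 0.78.

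**Step 3: allowance for baseline adjustment.** With one covariate and a single post measurement, the residual SD shrinks by √(1 − r²), so the smallest d with 80% power is 0.780 × √(1 − r²), keeping df = 58:

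| assumed r | √(1 − r²) | smallest d at 80% | power at d = 0.8 | power at d = 0.5 |
|---|---|---|---|---|
| 0.3 | 0.954 | 0.74 | 85% | 47% |
| 0.5 | 0.866 | 0.68 | 91% | 55% |
| 0.7 | 0.714 | 0.56 | 98% | 71% |

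This is only an approximation. The model in section 6.1 has two time points, two difficulty levels, the pre-score, age and sex. Its power cannot be computed from the SAP, which states no correlations.

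**Step 4: what a null result could exclude.** The 95% half-width for the group difference, in SD units, is 2.002 × √(1/40 + 1/20) × √(1 − r²) = 0.548 × √(1 − r²). This is 0.55 with no adjustment, and 0.52, 0.47 and 0.39 at r = 0.3, 0.5 and 0.7. Taking d = 0.5 as a moderate effect (an assumption), an estimate of exactly zero excludes it only if √(1 − r²) is below 0.5/0.548 = 0.912, that is, if r exceeds about 0.41.

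**The case against.** The strongest reply has four parts.

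*The planned analysis has more power than the t-test.* This stands in part. The approximation above gives 85% to 98% at d = 0.8 for r of 0.3 to 0.7, so there may be real reserve. But the SAP states no correlation and makes no claim that adjustment offsets a smaller effect.

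*0.8 may already be a cautious figure.* The SAP says that d was estimated from the cited findings and does not give the effect sizes in those studies. A reader might infer that 0.8 is the trained-task effect itself, and hence that 80% power requires nearly all of it (0.78/0.8, about 97.5%) to carry over to the n-back. The SAP does not support that. If the source effects were, as an assumption, 1.2, then d = 0.78 would need only 0.78/1.2 = 65%. No carry-over fraction can be stated, and this objection stands in full.

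*The reasoning may be in the protocol.* It may, and the absence of a fuller justification is not the point. The point is what section 1.4 itself states: a source concerning one kind of outcome and a power claim for another.

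*Little depends on it.* This is a phase II trial whose sample size is evidently fixed (section 2.1 already speaks of treatment in the past tense), and section 6.1 already plans marginal means with 95% confidence intervals. This limits the remedy to wording. It does not make the present power statement right.

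**Conclusion.** The concern holds in a limited form. The claim of at least 80% power for the primary outcome is not supported by its stated basis, because d was estimated from trained-task performance and the n-back is untrained. By the stated t-test the claim is true for a transfer effect of about 0.78 or more, and power falls to 58% at an assumed d of 0.6 and 43% at 0.5.

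Two stronger readings should be resisted. One is that 60 is miscalculated; it is not, given d = 0.8. The other is that the trial is underpowered. The SAP gives no transfer effect size and does not show that it lies below 0.8, and the power of the planned mixed model cannot be computed from what is given. The smaller values of d, the correlations and the choice of 0.5 as moderate are all assumptions made here to show the range. The point should be corrected because it concerns the primary endpoint and costs very little to put right.

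**What to change.** Keep N = 60 and the analysis. Replace the power statement in section 1.4 with text to this effect:

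> d = 0.8 was estimated from studies of trained-task performance. For the untrained n-back, N = 60 (40 vs 20) gives at least 80% power by t-test only for d of about 0.78 or more; power is 71%, 58%, 43% and 30% at assumed d = 0.7, 0.6, 0.5 and 0.4. Baseline adjustment may raise this (as a one-covariate approximation, smallest d about 0.74 to 0.56 for assumed pre-post correlations of 0.3 to 0.7). A non-significant primary result will be interpreted from the 95% CI of the group difference and not as evidence against a moderate transfer effect unless the CI excludes it.

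The cost is a few sentences, with no extra participants and no new analysis. The downside is that the stated power reads less favourably.

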2.1. Definitions

The **full analysis set** will consist of all randomized participants who received at least one day of intervention. If participants withdraw informed consent after baseline assessment, they will be considered screening failures and, therefore, will not be included in the full analysis set. The

per-protocol analysis set comprises all subjects who received the full three weeks of intervention or control intervention and completed all visits in the treatment groups they were allocated to. Safety outcomes [see Safety outcomes section (22)] are assessed during tDCS intervention, and all participants who received at least one intervention will be included in the safety analysis set according to their actual treatment. Since no participant received other treatment as intended or switched treatment groups during the study, and no information on safety measures is available for participants who missed intervention or follow-up visits or dropped out, the safety analysis set is the same as the per protocol analysis set in this study.

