1.1. Study design

This study is a monocentric, prospective, randomized, open-blinded endpoint (PROBE) (17) phase II clinical trial designed to evaluate the effectiveness of a cognitive training intervention compared to a control intervention [Progressive Muscle Relaxation; PMR (18)] in patients with post-COVID subjective or objective cognitive impairment (primary endpoint).

Patients with post-COVID cognitive impairment participate in a three-week intervention program consisting of nine sessions (three per week) of either cognitive training or PMR (18) (open-label interventions). In the cognitive training group, participants are further divided into two subgroups: half receive anodal tDCS while the other half receive sham tDCS in a double-blinded, sham-controlled manner (secondary endpoint). Thus, participants are randomly allocated to one of three study arms: (1) cognitive training with anodal tDCS over the left dorsolateral prefrontal cortex (DLPFC); (2) cognitive training with sham tDCS over the left DLPFC; or (3) PMR with sham tDCS.

Random allocation to these three groups is done through a stratified block randomization method with variable block length, using a 1:1:1 ratio. The stratification is based on participants' performance in the n-back task during pre-assessment, with two strata: those scoring $\leq 87\%$ correct and those scoring > 87% correct. The randomization sequences are generated software's blockrand package using the R (https://CRAN.Rproject.org/package=block- rand; http://www.R-project.org). Following a telephone screening and baseline assessment, eligible participants who provide written informed consent are randomly assigned to a study arm according to the generated randomization sequence within each block and performance stratum.

Secondary hypotheses related to the comparison of the two cognitive training arms with active or sham tDCS, will be evaluated in a double-blinded, sham-controlled manner.

[figure not shown]

Figure 1. Neuromod-COV study flowchart. tDCS: transcranial direct current stimulation; PMR: Progressive Muscle Relaxation. Obtained from Neuromod-COV study protocol (14).

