2.2. Application

The primary efficacy analysis will be done using the full analysis set, including estimated values from multiple imputations for missing values (Intention to treat). A sensitivity analysis of the primary outcome in the per-protocol analysis set will be conducted. The safety analysis will be done in the safety analysis set, which is the same as the per-protocol analysis set.

3. Trial centers

Participant recruitment takes place at one center: Universitätsmedizin Greifswald.

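### The primary analysis set leaves out randomised participants who never start an open-label intervention, so it is modified intention to treat and not the intention-to-treat set it is called

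*SAP*

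**What the plan says.** Four statements in the SAP bear on this point.

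- **Who is in the set (section 2.1).** The full analysis set "will consist of all randomized participants who received at least one day of intervention". A second rule follows: "If participants withdraw informed consent after baseline assessment, they will be considered screening failures", and these people are also left out of the set.
- **How the set is used and named (section 2.2).** "The primary efficacy analysis will be done using the full analysis set, including estimated values from multiple imputations for missing values (Intention to treat"). The only sensitivity analysis named for the primary outcome uses the per-protocol set.
- **Blinding (section 1.1).** Participants receive "either cognitive training or PMR (18) (open-label interventions"). Blinding applies within the training arms, where "half receive anodal tDCS while the other half receive sham tDCS in a double-blinded, sham-controlled manner". That contrast is secondary.
- **Timing (section 1.1 and Table 1).** "Following a telephone screening and baseline assessment, eligible participants who provide written informed consent are randomly assigned to a study arm". Randomisation is stratified on the pre-assessment n-back score, and Table 1 places pre-assessment (V1) three days before the first session.

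**The concern.** Entry to the primary set depends on something that happens after randomisation, namely receiving a first day of intervention. Leaving out never-treated participants does little harm when starting cannot depend on the arm. That argument could be made for the double-blind tDCS contrast, but not for training versus PMR. Someone who enrolled hoping for cognitive training and learns that they have been given relaxation may decline to begin, and the rule then removes that person from the primary analysis.

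Two things are at stake. The set can lose the balance that randomisation created, in the arm of only 20 where each participant is 5% of the total. And the intention-to-treat label tells readers that they have a protection which this set does not give.

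**Working it through.** **1. Can the arm influence who is analysed?** The stratifier is the pre-assessment n-back score, so allocation must follow V1, and V1 is three days before the first session. There is thus an interval between allocation and the event that admits a person to the set. The SAP does not say that the arm stays concealed until the first session.

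**2. Does anything else in the SAP restore non-starters?** No.
- The 30 imputations (section 5) are applied to the full analysis set, so they cannot bring back people outside it.
- The per-protocol set is narrower still.
- Section 2.1 states that nobody switched arm. It does not state that everyone randomised started.

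**3. The plan's own sample size.** Inputs from section 1.4: d = 0.8, two-sided alpha 0.05, 40 training and 20 PMR. A two-sample t-test (noncentral t) gives 81.9% power, and 60 is the smallest 2:1 total that reaches 80%. The figure of 60 reproduces and is not in question.

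**4. Shift in the raw PMR mean.** Suppose e of 20 PMR participants are excluded and their mean lies d SD from that of the rest. Then

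shift = (e/20) × d.

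Both e and d are assumptions. The type I error below is for an unadjusted t-test with no true effect.

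| e of 20 | d (SD) | Shift (SD) | Two-sided type I error |
|---|---|---|---|
| 0 | any | 0 | 5.0% |
| 2 | 0.5 | 0.05 | 5.3% |
| 2 | 1.0 | 0.10 | 6.4% |
| 3 | 1.0 | 0.15 | 8.0% |
| 4 | 1.0 | 0.20 | 10.2% |

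The direction is open. Losing poorer performers from PMR understates the training effect, and losing better ones inflates it.

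**5. What remains after the planned adjustment.** Section 6.1 adjusts for pre-assessment n-back, age and sex. Take one endpoint, a linear model and a pre-post correlation r. The adjusted shift is the outcome shift minus r times the baseline shift, in SD units.

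- *Starting depends on baseline only.* The outcome shift is r times the baseline shift, so the adjusted shift is 0.
- *Starting depends on the outcome itself.* The baseline shift is r times the outcome shift, so the adjusted shift is (1 − r²) times the raw shift.

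The SAP gives no r. With r = 0.6 assumed, 1 − 0.36 = 0.64, and 0.05 SD becomes 0.032 while 0.15 SD becomes 0.096. The factor is 0.91 for r = 0.3 and 0.51 for r = 0.7. A simplified ANCOVA simulation (40 versus 20, three PMR non-starters, no true effect, r = 0.6) agrees. The baseline-driven shift falls from 0.11 to about 0.00 SD, and the outcome-driven shift falls from 0.18 to 0.11 SD (0.18 × 0.64 = 0.115).

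**6. What MAR imputation of non-starters adds.** Add one further V1 measure, assumed to correlate 0.6 with the outcome and 0.5 with baseline n-back. Then R² = (0.36 + 0.36 − 2 × 0.36 × 0.5)/(1 − 0.25) = 0.36/0.75 = 0.48. The outcome-driven shift becomes 0.18 × 0.52 = 0.094 SD, and the simulation with 30 imputations gave 0.09 SD. The gain over adjustment alone is therefore small: 0.11 to 0.09 SD.

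**The case against.** The strongest reply is that the mechanism is assumed. The SAP does not say when the arm is disclosed. If participants learn it only at the first session, or if nobody fails to start, nothing is lost. The set is also defined openly, imputation covers dropouts after the first session, and the commitment to CONSORT reporting with a flow diagram (sections 1 and 3.1) should show exclusions by arm. All of this stands. It limits the claim to what the rule permits and says nothing about what happened. It does not make the label correct, and a flow diagram shows exclusions without putting anyone back into the analysis.

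Three stronger readings are tempting, and the SAP supports none of them.

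- *The primary estimate is biased by 0.05 to 0.20 SD.* Those are raw-mean shifts under invented numbers of non-starters. The planned covariates reduce them, to about zero if starting depends on baseline.
- *Analysing all randomised participants with imputation removes the bias.* Most non-starters would lack V11 data. MAR imputation would draw PMR non-starters' outcomes from PMR participants who were treated, so it cannot repair outcome-driven non-starting.
- *The rule costs power.* With two PMR non-starters excluded, power is 79.1%, and with three 77.5%. But that loss comes from missing outcomes. Imputing people who have no V11 data would recover little of it.

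A further fair point is that someone who declines PMR may well withdraw consent, and would then leave through the screening-failure sentence. Calling those people screening failures suggests that the authors had withdrawal before randomisation in mind, but the sentence has no end date and as written also covers later withdrawal. Changing only the one-day rule would leave that route open.

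**Conclusion.** The point holds as one about the definition and name of the primary set. A post-randomisation condition, in a comparison where the arm is visible, lets knowledge of the arm affect who is analysed. The set is modified intention to treat.

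The size of any bias cannot be found from the SAP. It is zero if everyone started. Otherwise the raw PMR mean shifts by (e/20) × d, for example 0.05 SD for two leavers at 0.5 SD, against a planned effect of 0.8 SD, and the adjusted estimate shifts by less. The reduced figures rest on an assumed pre-post correlation and a single-endpoint model, which is simpler than the planned mixed model.

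This should be changed. It is more than wording because no all-randomised analysis is planned, although one is feasible: the stratifier means that every randomised participant should have a pre-assessment n-back score.

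**What to change.** 1. Define the full analysis set as all randomised participants, in their allocated arm.
2. Limit the screening-failure sentence in section 2.1 to consent withdrawn before randomisation. Treat later withdrawals as missing data where use of their data is permitted.
3. Use any V11 and V12 data that non-starters provide. Otherwise include them in the 30 planned imputations, with V0 and V1 measures in the imputation model (n-back, letter updating, neuropsychological tests, PROMIS).
4. Report non-starters and withdrawals by arm.
5. If there are any non-starters, add a delta sensitivity analysis that moves their imputed scores away from MAR. A delta of 0.5 SD for 2 of 20 moves the PMR mean by (2/20) × 0.5 = 0.05 SD, so the effect on the conclusion is easy to read.
6. If the one-day set is kept, call it modified intention to treat and use it only as a sensitivity set.

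The cost is revised SAP wording, a few extra imputed records, slightly wider intervals, and reliance on the MAR assumption that section 5 already makes. The gain is mainly that the randomised comparison is kept and exclusions become visible. The point estimate may hardly move.

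### The consent-withdrawal rule for the full analysis set has no latest time, so read literally it also removes participants who were randomised and treated

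*SAP*

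**What the plan says.** Section 2.1 of the SAP sets membership of the full analysis set in two consecutive sentences. The definition sentence admits "all randomized participants who received at least one day of intervention". The withdrawal sentence then states: "If participants withdraw informed consent after baseline assessment, they will be considered screening failures", and gives the consequence: "and, therefore, will not be included in the full analysis set".

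Section 2.2 uses this set for the primary efficacy analysis, "including estimated values from multiple imputations for missing values (Intention to treat"). Section 5 specifies 30 imputed datasets, assuming data missing at random or completely at random. Section 6.2 uses the same set, with imputed data where values are missing, for all secondary analyses.

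On sequence, section 1.1 says: "Following a telephone screening and baseline assessment, eligible participants who provide written informed consent are randomly assigned to a study arm". Randomisation is stratified on "performance in the n-back task during pre-assessment". Table 1 places baseline and informed consent at V0, the pre-assessment at V1, the nine sessions at V2 to V10, the post-assessment (primary outcome) at V11 and the follow-up at V12.

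**The concern.** The withdrawal sentence says from when it applies but not until when. Since V0 precedes randomisation and treatment, its plain wording covers the whole randomised period. A participant who is randomised, attends at least one session and then withdraws consent is in the set by one sentence and out of it by the next.

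What is at stake is whether the primary analysis population is fixed in advance. Followed as written, the rule makes an exclusion depend on an event after randomisation. Section 1.1 describes the comparison as "cognitive training or PMR (18) (open-label interventions"), so participants know whether they are training or relaxing. Withdrawal, and with it removal from the analysis, could then differ between the groups. An intention-to-treat analysis is meant to avoid exclusions of this kind.

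**Working it through.** The check sets the two sentences of section 2.1 against the visit sequence. Inputs: baseline at V0, pre-assessment at V1, sessions at V2 to V10, post at V11 and follow-up at V12 (Table 1). Randomisation uses the V1 n-back score (section 1.1), so it falls after V1.

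| Consent withdrawn | By the definition sentence | By the withdrawal sentence, read literally | Agreement |
|---|---|---|---|
| After V0, before randomisation | Out: not randomised | Out | Yes |
| After randomisation, before the first session | Out: no day of intervention | Out | Yes |
| After the first session, before V11 | In: V11 value missing, imputed under section 5 | Out: not imputed | No |
| After V11, before V12 | In: V11 value observed, V12 missing | Out: observed primary value discarded | No |

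Two things follow.

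1. In the first two rows the withdrawal sentence does not alter membership, because the definition already excludes these people. It alters membership only in the last two rows, where it contradicts the definition.
2. In those two rows it also cuts across sections 2.2 and 5. Before V11 it bypasses the planned imputation. Between V11 and V12 it drops a primary outcome that was measured.

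No figure in the SAP sizes this. The nearest is the sample size in section 1.4, which reproduces. For 40 against 20 participants with d = 0.8 and two-sided alpha 0.05, the noncentrality is 0.8 × √(40 × 20 / 60) = 2.92 on 58 degrees of freedom. The power of the t-test is then 0.819, against the stated minimum of 80%. If, purely as an assumption, two PMR participants were lost (40 against 18), the noncentrality is 0.8 × √(40 × 18 / 58) = 2.82 on 56 degrees of freedom and the power is 0.791. This shows only that the trial is small enough for a few membership decisions to count. It does not measure the effect of the rule, because the number withdrawing is not given.

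**The case against.** The best defence is that the sentence limits itself. It excludes people because they are screening failures, and in ordinary usage someone who has been randomised and treated is not one. The order in section 1.1 fits: screening and baseline, then consent and randomisation. The plan also distinguishes the full set from a per-protocol set of completers and imputes missing values in the full set, so it evidently expects treated participants with incomplete visits to stay in. That the sentence is redundant on this reading proves little, since it may serve only to label people who left after V0.

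Much of this stands. It makes withdrawal before randomisation the probable meaning. It does not supply the missing end point: no section states one, and the label is assigned by the sentence itself to anyone who withdraws after V0. The scope of a rule for the primary analysis set should not have to be inferred from a label.

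Three stronger readings are tempting, and the document does not support them.

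- A reader might infer that treated participants have in fact been removed. Section 2.1 does mention "participants who missed intervention or follow-up visits or dropped out", but in explaining why safety data are lacking. It does not say that anyone withdrew consent after treatment or was excluded for it.
- A reader might fault the SAP for not separating dropping out from withdrawing consent. That distinction, and the use of data after withdrawal, are commonly left to the protocol and consent form, so their absence here is not a finding.
- A reader might take the power figures above as a loss caused by the rule. They rest on an assumed count. A participant whose V11 value is missing also adds little information on the primary outcome when kept and imputed.

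**Conclusion.** The concern holds as a defect of wording in a rule that governs the primary analysis set. Read literally, section 2.1 excludes randomised, treated participants who later withdraw consent, contrary to its own definition and to the intention-to-treat label in section 2.2. Because section 6.2 uses the same set, the secondary analyses inherit the defect.

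Its size is unknown. The SAP gives no number of withdrawals, and neither an exclusion nor a bias is shown. If nobody withdrew consent after the first session, the two sentences give the same set and nothing changes. The conclusion rests on the visit order in Table 1, on randomisation following the V1 n-back, and on the absence of a latest time anywhere in the SAP. Whether differential withdrawal would arise in this open-label comparison is a possibility, not something the document establishes. The wording should be corrected before the primary analysis because the probable intention is clear and the change is small.

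**What to change.** Limit the screening-failure rule in section 2.1 to consent withdrawn before randomisation. Add that randomised participants with at least one day of intervention who withdraw later remain in the full analysis set in their allocated arm. Data collected up to withdrawal are used as far as consent permits, and the remaining values are imputed as in section 5. Reporting the number of such withdrawals by arm would let readers judge whether they matter. Randomised participants who never start a session stay outside the set under the existing definition, which this change leaves alone.

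The cost is a sentence or two of SAP text. If such withdrawals occurred, there would be a few more imputed values and possibly slightly wider confidence intervals.
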